XII. Data Management

a. Data collection

All study data will be collected during both study visits. Study data to be collected includes clinical photography, Cherry images, OCT images and qualitative patient responses to treatment and laboratory results. Pain scores will be recorded on the case report form for visit 1, LFGS for screening visit, visit 1 and 2. Subjects' answers for satisfaction evaluation questions will be also recorded. All physical documentation and IRB correspondence will be stored in study binders maintained in restricted lab space only accessible by study staff and members of the [name] Lab. Digital data including photographs will be deidentified and stored on MGB computers. Any identifiable information in photographs such as eyes and tattoos will be blacked out and deidentified. All study documents containing PHI will be password encrypted, including the enrollment log and identification key. An encrypted external hard drive will be used to store the data as a backup.

b. Record retention

The Investigator or designees will retain all study records in accordance with the test facility's SOP's.

XIII. IRB Review and Approval

The study will not begin prior to the receipt of written confirmation of approval by the IRB and any relevant regulatory authority. It is the responsibility of the Investigator to obtain the IRB approval (per the U.S. Code of Federal Regulations, Title 21, Part 56 and applicable ICH guidelines) for the protocol, amendments, informed consent, subject information sheet, questionnaires, and advertising materials used to recruit study subjects, if appropriate.

XIV. REFERENCES

1. Uitto J. Understanding premature skin aging. *N Engl J Med.* 1997 Nov 13;337(20):1463-5.
2. Zouboulis ChC. Intrinsic skin aging. A critical appraisal of the role of hormones. *Hautarzt.* 2003 Sep;54(9):825-32.

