**Assessment and Augmentation of Lip Appearance in Specific Study
Populations**

NCT04839692

December 29, 2021

Assessment and Augmentation of Lip Appearance in Specific Study Populations

PRINCIPAL INVESTIGATORS:

[name], PhD
Cutaneous Biology Research Center (CBRC)
Massachusetts General Hospital Research Institute
[name]
[contact]
[contact]
e-mail: [contact]

CO- PRINCIPAL INVESTIGATOR:

[name], MSHS
Cutaneous Biology Research Center (CBRC)
Massachusetts General Hospital Research Institute
[name]
[contact]
[contact]
e-mail: [contact]

VERSION DATE

December 29,2021

TABLE OF CONTENTS

	Page
I. OBJECTIVE	3
II. BACKGROUND	3
III. AIMS	4
IV. SUBJECT SELECTION	
a. Inclusion Criteria	4
b. Exclusion Criteria	4
c. Source and recruitment of subjects	5
V. SUBJECT ENROLLMENT	
a. Method of enrollment	6
b. Informed consent form (ICF)	6
VI. STUDY PROCEDURES	6
a. Study visits and procedures	6
b. Drugs to be used	9
c. Devices to be used	9
d. Procedures/Interventions	10
e. Data to be collected and when data is collected	11
f. Remuneration	11
VII. BIOSTATISTICAL ANALYSIS	11
VIII. RISKS AND DISCOMFORTS	14
IX. POTENTIAL BENEFITS	
a. Potential benefits to subjects	15
b. Potential benefits to society.....	15
X. MONITORING AND QUALITY ASSURANCE	
a. Independent monitoring of source data	15
b. Safety monitoring	15
c. Outcome monitoring	16
d. Adverse Event reporting.....	16
XII. Data Management	
a. Data collection	17
b. Record retention	17
XIII. IRB Review and Approval	17
XIV. References	18
Appendix A (Study Schema)	19

I. OBJECTIVES

The objectives of this study are:

- To determine the effects of aging on the lips and perioral area by comparing quantitative changes in lip; and
- To validate the role of optical coherence tomography (OCT) in investigating lip microcirculation; and
- To evaluate any volume, color and texture change of the lips pre and post treatment
- To investigate pain levels from lip filler treatment

To achieve the objectives, the study aims to obtain data from two specific study populations, including:

- 1) Aged females, otherwise healthy (≥ 60 years);
- 2) Young females, otherwise healthy (21-30 years)

II. BACKGROUND

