Skin aging is a complex biological process mainly influenced by two independent mechanisms, intrinsic and extrinsic skin aging [1]. Intrinsic skin aging is determined primarily by inherent genetic factors, hormonal status, cellular metabolism and function [2]. It represents degenerative aging processes seen in other organ systems as a consequence of the passage of time. Extrinsic skin aging results from various external influences including solar UV radiation, health and lifestyle factors, such as tobacco smoking, environmental pollution, and other systemic conditions, such as diabetes and renal insufficiency [3-5].

In skin with chronic exposure to UV radiation, termed photoaging, alterations in skin structure and function depend primarily on the degree of sun exposure and baseline skin pigment. UV radiation induces collagen breakdown. Diminution of collagen framework that supports vascular plexus within the skin leads to broken vessels [8]. The Langerhans cell population representing immune system of the skin is found to be reduced after chronic exposure to UV radiation contributing to impaired immune response to antigen and skin cancer cells [6,7].

These age-related changes caused by chronic sun exposure have not been well-documented in the lips [10]. The majority of literature on the aging lip has focused on volume loss. Hyaluronic-acid based fillers have been used primarily for volume augmentation, but their effect on lip color and texture has seldom been defined [9,12].

We propose to study aging of the cutaneous changes of human skin anatomy in the lips and perioral area to better understand and quantify the aging process in this, including the effect of age on lip redness.

We also aim to test the effects of a common lip augmentation procedure, hyaluronic-acid based fillers, on the appearance of aging lips, in addition to the tolerability of this procedure. We hypothesize that dermal lip fillers may decrease the redness of the lips.

Besides, we want to evaluate oxytocin level changes and relate it to subjects' satisfaction with procedure.

The study will take place at MGH's Clinical Unit for Research Trials & Outcomes in Skin (CURTIS) at [name] or Translational Clinical Research Center (TCRC) on the 12th floor of the White Building.

III. Specific AIMS

To:

- Compare the changes in skin anatomy due to intrinsic aging
- Correlate clinical assessment with OCT imaging;

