- Compare changes in lip color, texture and volume before and after filler with non-invasive imaging, including digital photography, OCT and three-dimensional imaging
- To assess the tolerability of lip filler by evaluating pain level from lip filler treatment at initial insertion and overall procedural pain
- To evaluate how oxytocin levels change during and after an aesthetic procedure.
- To assess lip color change after the procedure.
- To evaluate patient satisfaction related to the procedure.

IV. SUBJECT SELECTION

Subjects will be screened to determine if they meet all the eligibility criteria specified below. We will recruit and screen up to 50 subjects with the goal of 40 subjects enroll and complete the study (20 per study arm).

a. Inclusion Criteria

1. Subjects must be able and willing to provide written informed consent and comply with the requirements of the study protocol;
2. In good general health, based on answers provided during the screening visit;
3. Subjects must be able to read and understand English;
4. Female subjects;
5. Aged 21-30 years and Post menopausal women;
6. Skin Types (Fitzpatrick Skin Phototypes I-VI);

* Smoking history is self-report.

7. Have very thin to moderately thick lips (Lip Fullness Grading Scale [LFGS] scores 0–2).

b. Exclusion Criteria

1. Participation in another investigational drug or device clinical trial in the past 30 days;
2. Are pregnant or lactating;
3. Intake of hormone replacement therapy (HRT) in the past 6 months;
4. Have a history of drug or alcohol abuse or have reported habitual alcohol intake greater than 2 standard drinks per day [e.g., 2 beers, 2 glasses of wine, or 2 mixed drinks];
5. Presence of eczema, psoriasis, or any other skin disease on the lips or perioral skin;
6. Have birth marks, tattoos, scars, or any other disfiguration of the skin in the skin area of interest;
7. Use of any anti-aging skin care products containing retinoic acid, retinol, or other retinoids (e.g. tazarotene, adapalene) or estrogen on the skin area of interest in the past 6 months;
8. Use of any prescription topical medication, such as corticosteroids or hydroquinone on the skin area of interest in the past 6 months;
9. Have a history of photodynamic therapy treatment or any skin rejuvenation procedure on the skin area of interest;
10. History of blood-clotting abnormality;
11. History of keloid formation or hypertrophic scarring;

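### The objectives define the older cohort as women of 60 or over, but inclusion criterion 5 admits any post-menopausal woman with no lower age

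*Combined protocol and SAP*

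**What the plan says.** Section I (Objectives) says the study will draw on two populations. The older one is given as "Aged females, otherwise healthy (≥ 60 years"; the younger one is healthy women of 21 to 30. Menopausal status is not mentioned there.

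Section IV.a, criterion 5, which governs entry, reads "Aged 21-30 years and Post menopausal women". The older group is identified by menopausal status alone.

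The two groups are meant to be compared. The first objective is "To determine the effects of aging on the lips and perioral area by comparing quantitative changes in lip", the first specific aim (section III) is "Compare the changes in skin anatomy due to intrinsic aging", and the Background states an interest in the aging process "including the effect of age on lip redness". Section VII.b adds that the OCT capillary metrics will be used for comparisons between cohorts as well as within them. The size is set in section IV: "with the goal of 40 subjects enroll and complete the study (20 per study arm".

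**The concern.** A comparison of young with older women needs one definition of older. Here the stated target population and the operative entry rule differ, and the entry rule is the wider of the two over the ages that matter. A site that follows the criteria exactly can fill part of the older arm with women whom the Objectives do not describe.

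What is at stake is interpretation. As the protocol stands, a reader cannot tell whether an aging result on lip anatomy, redness or microvasculature would describe women of 60 or over, or post-menopausal women in general. If aging effects build up gradually, younger post-menopausal women would also dilute the contrast.

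**Working it through.** **Side-by-side check of every place that could set an age**

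| Place | What it sets for the older group |
|---|---|
| I. Objectives | Age 60 or over; menopause not mentioned |
| IV.a, criterion 5 | Post-menopausal; no lower age |
| IV.a, other inclusion criteria | No age |
| IV.b, exclusions 1 to 16 | No age |
| IV.c, telephone prescreen | Refers to a required age range, gives no number |
| VI.a, screening visit and Visit 1 | Refers back to the inclusion and exclusion criteria |
| Appendix A, schema | Refers back to the inclusion and exclusion criteria |

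Section VI.a lets women who meet the listed criteria enroll, so criterion 5 is the working rule. Above the young range, the ages outside both populations in the Objectives are 31 to 59. A post-menopausal woman of those ages passes criterion 5, so the two definitions select different sets of women.

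Criterion 5 has a second wording fault. It joins its two groups with *and*, while section IV requires all criteria to be met. Read literally, a woman would have to be both 21 to 30 and post-menopausal. Given the two populations in the Objectives, alternatives are evidently meant.

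**Does the text show which definition was intended?** The Background points both ways. It says "Intrinsic skin aging is determined primarily by inherent genetic factors, hormonal status, cellular metabolism and function", which would support a menopausal definition, and then "It represents degenerative aging processes seen in other organ systems as a consequence of the passage of time", which would support an age definition. Exclusion 3 (recent hormone replacement therapy) and exclusion 7 (topical estrogen, among other products) show some attention to hormones but do not state how the older cohort is defined.

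**Bound on dilution.** The plan gives no figure to reproduce: no age distribution, effect size or standard deviation. The following is a bound under stated assumptions.

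- n = 20 women in the older arm (section IV).
- k = number of them under 60. This is assumed; criterion 5 permits 0 to 20.
- D = difference in means between women of 60 or over and young women.
- g = share of D already present in the under-60 women, assumed to lie between 0 and 1.

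The observed older-minus-young difference is [(20 − k)·D + k·g·D] / 20, so the share of D retained is 1 − (k/20)(1 − g).

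| k (assumed) | Retained, g = 0 | Retained, g = 0.5 | Retained, g = 1 | 60-plus subset |
|---|---|---|---|---|
| 1 | 1 − 0.05 = 0.95 | 0.975 | 1.00 | 19 |
| 5 | 1 − 0.25 = 0.75 | 0.875 | 1.00 | 15 |
| 10 | 1 − 0.50 = 0.50 | 0.75 | 1.00 | 10 |
| 20 (limit) | 1 − 1.00 = 0 | 0.50 | 1.00 | 0 |

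There is no loss if the change is complete by menopause (g = 1). The largest loss occurs if none of it has happened before 60 (g = 0).

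**The case against.** The strongest reply is that the two statements can be applied together. The Objectives describe who is sought, criterion 5 adds an entry condition, and a post-menopausal woman of 60 or over satisfies both. The prescreen asks about age, not menopause, and the only number the documents offer for older women is 60, so staff may well apply it. This narrows the gap in practice but does not close it: the prescreen states no number, and the criteria on which enrollment depends contain no floor.

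A second reply is that little depends on it. Section VII.c promises only descriptive summaries before and after treatment, the only cross-cohort analysis text is one clause on OCT metrics, and a table of ages in the report would show who was studied. Much of this stands. No error rate or power is affected, and the filler, pain, oxytocin and satisfaction outcomes are compared within subject. But the aging comparison is the first objective and the first aim, and a descriptive comparison still needs a defined population. An age table would reveal a mixed cohort after the fact without saying which group the study set out to describe.

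A third reply is that the dilution figures rest on chosen counts and on a summary by means, which the plan does not specify. That is correct. They show how the effect scales and do not estimate it.

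**Conclusion.** The concern holds. The Objectives and criterion 5 contradict each other on who belongs to the older cohort, nothing else in the document resolves it, and the entry rule as written admits women of 31 to 59 who are in neither stated population. The contradiction itself is certain from the text.

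Its effect on results is not known. Each woman under 60 would be 1/20 = 5% of the older arm. The contrast would shrink by 0 to 5% with 1 such woman, 0 to 25% with 5 and 0 to 50% with 10. These ranges assume the counts and assume that the under-60 mean lies between the young and 60-plus means. The documents do not show whether any such woman was or will be enrolled. The point should be fixed because it reaches the first objective; it does not threaten the within-subject filler findings.

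**What to change.** Reconcile section I with criterion 5 by choosing one definition of the older cohort. Use it in the Objectives, in criterion 5 (worded as two alternative groups) and in the prescreen, with the age range written as a number if age is the criterion. The choice is the sponsor's:

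- If 60 or over is kept, add that floor to criterion 5.
- If menopausal status is intended, state how it is established, which the protocol does not do, and restate the objective and the eventual conclusion to match.

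If women under 60 are already enrolled, report the age distribution of the older arm and give the descriptive aging comparison for the 60-plus subset beside that for all older women. Keep every treated woman in the within-subject filler, pain and oxytocin summaries.

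The cost is an IRB-approved amendment (section XIII) and an edit to the prescreen script and possibly the recruitment posting. No new data should be needed, because demographics are reviewed at screening. The downsides are a somewhat narrower recruitment pool if the floor is kept, and less precision in the subset: 15 or 10 women if 5 or 10 of the 20 are under 60, and no subset to report in the limiting case where all are.

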The Cherry Imaging system is a 3-dimensional photographic imaging system designed to accurately measure aesthetic treatments to deliver objective patient data before and after aesthetic treatments. The handheld camera captures thousands of three-dimensional images of the face and/or body from multiple field views and angles that

are analyzed to provide 100-micron accuracy level data of the body and/or face for real-time evaluation of treatment results and traceability over time. The Cherry Imaging device will be used to take images of the face before the filler treatment takes place and during the last visit. No special lighting is needed for the imaging device, so the images will be taken and processed directly in the room where the filler procedure will take place. The Cherry imaging software has multiple capabilities, including the ability to calculate topographic changes, volume changes, and color changes in the skin.

d. Procedures/Interventions

Optical coherence tomography (OCT) imaging

The OCT imaging system will be cleansed with 70% isopropyl alcohol wipe in patient's presence prior to perform any imaging procedure. The subject's lips and surrounding skin at the intended OCT imaging sites will be cleansed with 70% isopropyl alcohol prep and allowed air dry thoroughly. First, OCT imaging will be performed in non-contact setting focused on the skin surface to image its profile. It takes about 1-2 minutes to properly position the patient and align OCT device per site and about 30 seconds per scan.

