Secondly, a z-spacer (OCT-Imm03, ThorLabs, Inc., Newton, NJ) will be attached to the OCT probe and glycerol will be utilized for optical coupling (immersion) between the OCT spacer and the skin. In this setting, a sequence of three OCT angiographic images will be acquired. For imaging of the lips, a waterproof film polymer (i.e., Tegaderm) dressing will be used to minimize direct contact of the OCT spacer with the skin. Glycerol will be applied to the lips with a Q-tip. The middle portion of the bottom part of the lip will be imaged on each patient. One image will be taken. Then the OCT imaging device will be pressed onto the skin until the skin is blanched. When the skin is blanched, a second OCT image will be acquired. After the second image is acquired, the pressure will be held with the skin blanched for a further 60 seconds and then released. A third image will be taken about 10 seconds after pressure is released. The pressure required for blanching the skin will be measured and recorded. A brief test may be done near the imaging site prior to imaging in order to determine the blanching threshold pressure. The acquisition and saving time per image will be less than 1 minute. Taking these three images will allow assessment of the vascular density and vessel thickness as well as the vessel refilling characteristics after occlusion. If study staff operating the OCT imaging device decide the images are of too low quality or contain artifacts that would affect analysis, this procedure may be repeated on an area of the skin within close proximity to the original imaging location but at least 2-3 cm away from the original location. After finishing the OCT imaging procedures, the z-spacer will be detached and cleansed with 70% isopropyl alcohol wipe then allowed to air dry thoroughly prior to next use.

Cherry Imaging Photography

The Cherry Imaging system will be used to take images of the lips. The Cherry Imaging photography can take place at the MGH's Clinical Unit for Research Trials & Outcomes in Skin (CURTIS) or Translational Clinical Research Center (TCRC) since there is no special background or lighting condition needed to use the Cherry Imaging system.

Digital Photography

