- Immediately after the filler procedure, approximately 3 cc of blood will be drawn into EDTA tubes containing Aprotinin supplied by the Brigham Research Core lab.
- after the after the "mirror reveal" (when we show the lips to the subject using a mirror approximately 3 cc of blood will be drawn into EDTA tubes containing Aprotinin supplied by the Brigham Research Core lab.

- 30-35 minutes after the filler procedure has been concluded, a final approximate of 3 cc of blood will be drawn into EDTA tubes containing Aprotinin supplied by the Brigham Research Core lab.

Each sample will be allowed to clot for 30-60 minutes at room temperature to prepare serum, then centrifuged at 1600 x g for 15 minutes at 4°C by study staff, and the serum will be transferred to plastic tubes.

The samples will be placed on dry ice and hand-delivered by the research staff to the Brigham Research Core lab or stored at -80 degrees freezer located at the MGH Navy Yard in the [name] lab when immediate delivery is not possible.

The Brigham Research Core lab will process the ELISA assay to evaluate oxytocin levels.

e. Data to be collected and when data is collected

Study data will be collected during each study visit. Study data to be collected includes OCT imaging (various images as described above, visit 1 and 2), digital photography and Cherry Imaging of the lips and perioral area (visit 1 and 2), visual assessment of treated area (visit 2), video recording (optional) from subject's reaction after the mirror reveal, Lip volume assessment with Lip Fullness Grading Scale (screening visit, visit 1 and 2), pain assessment of initial injection and overall procedure (visit 1), blood samples (visit 1) and satisfaction questionnaire answers (visit 1 and 2). Medical history and medications will be documented at visit 1. There are no other biological data or health information to be collected in this study.

Information about side effects in the treatment area or any adverse events will be collected during the follow-up call and visits.

f. Remuneration

Subjects will be paid \$50 for completing all imaging activities and filler treatment during visit 1, and \$100 for completing visit 2. The total remuneration amount is \$150 upon completing the study. We will provide a parking voucher at MGH main campus for each visit upon request.

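### A repeated OCT sequence may be taken 2-3 cm or more from the fixed mid-lower-lip site, and the protocol does not require the moved position to be recorded, reused or flagged

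*Combined protocol and SAP*

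**What the plan says.** Section VI.d (OCT imaging) names one site: "The middle portion of the bottom part of the lip will be imaged on each patient". Three contact images are taken there: before pressure, during blanching, and about 10 seconds after release. On the hold it says: "After the second image is acquired, the pressure will be held with the skin blanched for a further 60 seconds and then released". On what is written down it says: "The pressure required for blanching the skin will be measured and recorded".

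If the operator judges the images too poor or too affected by artifact, the procedure may be repeated on an area of skin "within close proximity to the original imaging location but at least 2-3 cm away from the original location".

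Other sections bear on how those images are used:

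- Sections VI.c and VII.b give a lateral field of view of 6 x 6 mm.
- Section VI.e schedules OCT at Visits 1 and 2 and lists no item for scan position.
- Section VII.b labels OCT files with the subject number. It derives vessel area, length, fractal dimension and curvature, for use within and between cohorts.
- Section III includes this aim: "Compare changes in lip color, texture and volume before and after filler with non-invasive imaging, including digital photography, OCT and three-dimensional imaging".
- Section VII.c plans descriptive pre/post summaries only.
- Section IV aims for 20 completers per group.

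**The concern.** A before/after comparison of a small capillary field depends on imaging the same place twice. The planned site provides this at the level of a region, because the same part of the lip is named for every patient and both visits. The repeat clause breaks the link. It sends the second attempt elsewhere and sets only a lower limit on distance, itself given as a range. Nothing ties the new position to the other visit.

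If the repeat is the scan analysed, a subject relocated at one visit contributes a change made up of any filler effect plus the difference between two sites. A subject relocated at both visits is still unmatched unless the same position is used twice. Relocated scans also enter the young/older comparison alongside mid-lip scans. Without a recorded position, the affected subjects could not be reliably identified when the summaries are prepared.

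**Working it through.** The plan states no figure to reproduce: there is no repeat rate, site effect, SD or power calculation for OCT.

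**1. Does a relocated field overlap the planned one?** Inputs from the protocol: field 6 x 6 mm, displacement at least 20-30 mm.

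- Displacement in field widths: 20/6 = 3.3; 30/6 = 5.0.
- Gap between fields along one axis: 20 - 6 = 14 mm and 30 - 6 = 24 mm if measured centre to centre; 20 and 30 mm if measured edge to edge.
- The field diagonal is 6 x sqrt(2) = 8.5 mm, so fields with centres 20 mm apart cannot overlap in any orientation.
- Relocation in opposite directions at the two visits would put the sites 2 x 20 = 40 to 2 x 30 = 60 mm apart.

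**2. Does it leave the lip?** For a sideways move from the midline, centre to centre, the whole field stays on the lip only if the lower lip is at least 2 x (20 + 3) = 46 mm or 2 x (30 + 3) = 66 mm wide. The protocol gives no lip width, so this stays open.

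**3. Is the position captured anywhere?**

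| Section | What it covers | Rule for a relocated scan |
|---|---|---|
| VI.d | Blanching pressure recorded | None |
| VI.e | OCT images at both visits | None |
| VII.b | Files labelled by subject number | None |
| VII.c | Descriptive pre/post summaries | None |
| X.a | General monitoring of procedures and records | None |
| XII.a | OCT images; pain, LFGS and questionnaire entries | None |

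No section says whether the repeat replaces the first scan.

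**4. Shift in mean change (all rates and effects assumed).** Let a and b be the shares of a 20-subject cohort relocated at Visit 1 only and at Visit 2 only. Let d be a constant site effect in SDs of the matched change.

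- Bias in mean change = (b - a) x d.
- Lowest case, 1 of 20 at d = 0.25: 0.05 x 0.25 = 0.0125 SD.
- Highest case, 4 of 20 at the same visit, d = 1: 0.20 x 1 = 0.20 SD.
- Standard error of the mean change without relocation: 1/sqrt(20) = 0.224 SD.
- Ratios: 0.0125/0.224 = 0.06; 0.20/0.224 = 0.89.

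**5. Spread of the change.** SD multiplier = sqrt(1 + (a + b)d² - (b - a)²d²).

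- Two subjects at each visit, d = 1: bias 0, multiplier sqrt(1.20) = 1.095.
- Four subjects at one visit, d = 1: multiplier sqrt(1.16) = 1.077.

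**6. Young/older comparison.** With an equal assumed relocation rate p in both cohorts, the expected bias is zero. The SD of the error from chance imbalance is d x sqrt(2p(1 - p)/20), with d now in between-subject SDs.

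- p = 0.05, d = 0.25: 0.017.
- p = 0.20, d = 1: 0.126.

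**The case against.** **The clause may be general wording.** It speaks of skin rather than lip, and section VI.d elsewhere refers to surrounding skin, to imaging sites in the plural and to set-up time for each one ("It takes about 1-2 minutes to properly position the patient and align OCT device per site and about 30 seconds per scan"). This is a fair reading and lowers confidence. It does not settle the matter, because the mid-lower lip is the only site named and the clause does not exempt it.

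**The distance may be deliberate.** The third image assesses refilling after occlusion, so an early repeat on the same tissue could carry over the first hold. That is plausible, although the protocol gives no reason. It also permits a pressure test with no minimum distance: "A brief test may be done near the imaging site prior to imaging in order to determine the blanching threshold pressure". That test is brief and serves only to find a threshold, so it says little against the recovery argument. A good reason for moving would still leave the position to be recorded and matched.

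**The consequence is conditional.** The repeat is optional, its frequency is unknown, and the first scan might still be the one analysed. A worksheet outside the document may capture position. All of this stands: the text shows that unmatched scans can enter the summaries, not that they do.

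**Non-relocated scans are not exactly matched either.** No landmark is given for placing a 6 mm field within the mid-lower lip, and about 1 mL of filler is injected between visits. This also stands. Planned-site pairs are matched by region only, so a matched-only summary reduces the problem without removing it.

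**Conclusion.** The gap is real and its weight is minor. Following the repeat clause can produce Visit 1/Visit 2 pairs from different tissue, and the document has no means of identifying them. This rests on the relocated scan being the one analysed.

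The non-overlap follows from the protocol's own figures. The bias figures do not: they assume 1 to 4 of 20 subjects relocated at the same visit and a constant site effect of 0.25 to 1 SD. Within that range the mean change shifts by 0.01 to 0.20 SD, or 0.06 to 0.89 standard errors. The limit of one standard error belongs to the assumed range; 5 of 20 at 1 SD would give 0.25 SD, just above it. Balanced relocation removes the mean shift and widens the SD by about 10% in the case shown.

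A reader might infer more than the document supports:

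- **That the clause is a flat contradiction.** It is loose, using a range as a minimum with no upper limit, but nearby and at least 2-3 cm away can both be true.
- **That repeats necessarily leave the lip.** This depends on lip width, which is not given.
- **That the young/older comparison is biased.** Nothing suggests that relocation differs by cohort.
- **That an error rate is at risk.** The plan is descriptive and specifies no test.
- **That a repeat must be made at the same site.** The protocol gives no recovery time or criterion on which to base such a rule.

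**What to change.** - Reconcile the repeat clause in section VI.d with the fixed mid-lower-lip site, and state whether a repeat replaces the first scan in the analysis. Whether to repeat at the same site after recovery is for the investigators to decide.
- For every relocated scan, record the position (side and distance from the midline) and a repeat flag.
- When relocation occurs at Visit 1, use the same position at Visit 2.
- Flag subjects whose two visits are not site-matched, including those first relocated at Visit 2, who cannot be matched afterwards.
- In section VII, report the OCT change with and without unmatched subjects, and the cohort summaries with and without relocated scans.

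The cost is a revised clause, a position-and-repeat entry on the OCT form and one extra summary line, with slightly fewer subjects in the matched-only summary. If an existing worksheet already captures position, a cross-reference covers the recording part.
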